## **11. Data Reporting / Regulatory Considerations**

### **11.1 Data Collection**

The data collection plan for this study is to utilize REDCap to capture all research intervention procedures outlined in the protocol, toxicity, efficacy, and adverse event data for all enrolled study participants. To ensure maximum compliance, subjects will be prompted by email, phone, or with a text message to their mobile phone. To ensure HIPAA compliance, text messages will only read as "A new survey is due." Participants will be informed of this prompting protocol beforehand. No PHI, or any details of medical therapy, will be revealed in the text message or in the surveys administered through REDCap (please see the survey attachment to review how each survey will appear). Texts will be sent from a study dedicated phone controlled by the study staff. The study phone will be encrypted and managed by ITS per WCM regulation. Subjects will complete surveys at the following intervals: every 8 hours post-operative day 1 and 2, Every 12 hours post-operative day 3 through 7.

### **11.1.1 REDCap**

REDCap (Research Electronic Data Capture) is a free data management software system that is fully supported by the Weill-Cornell Medical Center CTSC. It is a tool for the creation of customized, secure data management systems that include Web-based data-entry forms, reporting tools, and a full array of security features including user and group based privileges, authentication using institution LDAP system, with a full audit trail of data manipulation and export procedures. REDCap is maintained on CTSC-owned servers that are backed up nightly and support encrypted (SSL-based) connections. Nationally, the software is developed, enhanced and supported through a multi-institutional consortium led by the Vanderbilt University CTSA.

## **11.2 Regulatory Considerations**

### **11.2.1 Institutional Review Board/Ethics Committee Approval**

As required by local regulations, the Investigator will ensure all legal aspects are covered, and approval of the appropriate regulatory bodies obtained, before study initiation.

Before initiation of the study at each study center, the protocol, the ICF, other written material given to the study participants, and any other relevant study documentation will be submitted to the appropriate Ethics Committee. Written approval of the study and all relevant study information must be obtained before the study center can be initiated or the IP is released to the Investigator. Any necessary extensions or renewals of IRB approval must be obtained for changes to the study, such as amendments to the protocol, the ICF, or other study documentation. The written approval of the IRB together with the approved ICF must be filed in the study files.

The Principal Investigator will report promptly to the IRB any new information that may adversely affect the safety of the study participants or the conduct of the study. The Investigator will submit written summaries of the study status to the IRB as required. On completion of the study, the IRB will be notified that the study has ended.

All agreed protocol amendments will be clearly recorded on a protocol amendment form and will be signed and dated by the original protocol approving signatories. All protocol amendments will be submitted to the relevant institutional IRB for approval before implementation, as required by local regulations. The only exception will be when the amendment is necessary to eliminate an immediate hazard to the trial participants. In this case, the necessary action will be taken first, with the relevant protocol amendment following shortly thereafter.

Once protocol amendments or consent form modifications are implemented at the lead site, Weill Cornell Medicine, updated documents will be provided to participating sites, as applicable. Weill Cornell Medicine must approve all consent form changes prior to local IRB submission.

Relevant study documentation will be submitted to the regulatory authorities of the participating countries, according to local/national requirements, for review and approval before the beginning of the study. On completion of the study, the regulatory authorities will be notified that the study has ended.

### **11.2.2 Ethical Conduct of the Study**

The Investigators and all parties involved should conduct this study in adherence to the ethical principles based on the Declaration of Helsinki, GCP, ICH guidelines and the applicable national and local laws and regulatory requirements.

This study will be conducted under a protocol reviewed and approved by the applicable ethics committees and investigations will be undertaken by scientifically and medically qualified persons, where the benefits of the study are in proportion to the risks.

### **11.2.3 Informed Consent**

The investigator or qualified designee must obtain documented consent according to ICH-GCP and local regulations, as applicable, from each potential subject or each subject's legally authorized representative prior to participating in the research study. Subjects who agree to participate will sign the approved informed consent form and will be provided a copy of the signed document.

The initial ICF, any subsequent revised written ICF and any written information provided to the subject must be approved by IRB prior to use. The ICF will adhere to IRB requirements, applicable laws and regulations.

### **11.2.4 Compliance with Trial Registration and Results Posting Requirements**

Under the terms of the Food and Drug Administration Modernization Act (FDAMA) and the Food and Drug Administration Amendments Act (FDAAA), the Sponsor-Investigator of the trial is solely responsible for determining whether the trial and its results are subject to the requirements for submission to <http://www.clinicaltrials.gov>. Information posted will allow subjects to identify potentially appropriate trials for their disease conditions and pursue participation by calling a central contact number for further information on appropriate trial locations and trial site contact information.

### **11.2.5 Record Retention**

Essential documents are those documents that individually and collectively permit evaluation of the study and quality of the data produced. After completion of the study, all documents and data relating to the study will be kept in an orderly manner by the Investigator in a secure study file. In addition, all subjects' medical records and other source documentation will be kept for the maximum time permitted by the hospital, institution, or medical practice. Research records will be kept for at six years after the end of the study.

## **12. Statistical Considerations**

### **12.1 Study Design/Endpoints**

The study will be a randomized double blind placebo controlled trial. We will randomize 86 study participants into two arms, with equal numbers in each arm.

Both the control arm and intervention arm will receive medication to be taken 2 hours before surgery as well as for three days three times a day after surgery. The team will be blinded to medication each study participant is receiving and will be recorded using a subject coded system.

Participants will receive reduced oxycodone prescriptions (quantity to be determined by clinical practice and prescribing surgeon) as needed, as well as celecoxib and acetaminophen to be taken as prescribed for the peri-operative period and up to 7 days post-operatively.

During the 7 subsequent post-op days participants in both the intervention and control arms will be asked to maintain a pain diary. The diary will be implemented online through the REDCap platform, which allows for secure online surveys. To ensure maximum compliance, subjects will be prompted by email, phone, or with a text message to their mobile phone. To ensure HIPAA compliance, text messages will only read as "A new survey is due." Participants will be informed of this prompting protocol beforehand. No PHI, or any details of medical therapy, will be revealed in the text message or in the surveys administered through REDCap (please see the survey attachment to review how each survey will appear). Texts will be sent from a study dedicated phone controlled by the study staff. The study phone will be encrypted and managed by ITS per WCM regulation. Subjects will complete surveys at the following intervals: every 8 hours post-operative day 1 and 2, Every 12 hours post-operative day 3 through 7.

Participants will be monitored for adverse events by the pre-operative nurses as well as the post-operative anesthesia care nurses who will be counselled on symptoms to examine for. Participants will have the opportunity to document any adverse events on their surveys.

Our primary endpoint will be to compare participant reported pain between participants receiving gabapentin and those receiving placebo in addition to standard of care. This will be assessed using the 11-point numerical pain rating scales (NRS-11) from post-operative day 1 to 7.

Our secondary endpoints include narcotic use following surgery including the number of tablets taken, frequency and time when narcotic is initially utilized. Participant satisfaction will be documented. Reduction in other symptoms such as nausea will also be recorded.

## **12.2 Statistical Analysis**

The primary objective of this double-blind, placebo controlled randomized trial is to compare the participant-reported pain scores taken on an 11-point numerical rating scale (NRS-11) between subjects who received Gabapentin and controls who received placebo on day-7 post-scrotal surgery. The secondary objective is to determine whether the addition of gabapentin for post-operative pain control reduces narcotic intake. This study will also explore the effect gabapentin has on symptom modification.

Assuming a baseline NRS-11 score of 3.8 (from previous study) and a goal is to detect a two-point difference (reduction) in the day-7 pain score between the two groups, a sample size of 86 participants (43 per arm) will yield a power of 80% when using a two-sample t-test with a 0.05 two-

sided significance level. To account for potential loss to follow up and drop-out at a rate of 25%, each arm will require 43 study participants for a total recruitment of 86 study participants. This calculation assumes a standard deviation of 2.9, which is based on a previous study that looked at the effect of celecoxib in the same patient setting.

Approximately 150 to 250 microTESE procedures are conducted at our site annually. As a result, we plan to accrue and complete the study in 29 months (i.e. ~9 study participants per month).

Descriptive statistics will be calculated to describe the cohort of study participants using N (%) and mean, median, range for categorical and continuous factors, respectively. A two-sample t-test or nonparametric Wilcoxon rank-sum test will be used, as appropriate, to compare the mean (median) participant-reported pain scores on day 7 post-scrotal surgery between the two arms. A chi-square test or Fisher's exact test will be used, as appropriate, to compare the proportion of narcotic use post-scrotal surgery between the two arms and to compare the proportion of adverse events experienced post-scrotal surgery between the two arms. Similar analyses will also be completed on the NRS-11 pain score, narcotic use, and reported adverse events on day-1 post-scrotal surgery. Generalized estimating equations (GEE) modeling will also be performed to compare NRS pain scores, assessed over all post-operative days 1 to 7, between the gabapentin and placebo groups. GEE allows for multiple observations per participant (i.e., pain scores for day 1 to day 7, per participant) and also allows for the incorporation of missing pain scores at some of the defined time points.

All p-values will be two-sided with statistical significance evaluated at the 0.05 alpha level. Ninety-five percent confidence intervals for all parameters of interest will be calculated to assess the precision of the obtained estimates. All analyses will be performed in R Version 3.6.1 (R Foundation for Statistical Computing, Vienna, Austria). Note: The statistical considerations section was written in conjunction with [name], MS, in the Division of Biostatistics and Epidemiology, Department of Healthcare Policy & Research.

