### 1.1 Schema

## 1.2 Study Objectives

### 1.2.1 Primary Objectives

To compare participant reported pain between participants receiving gabapentin and those receiving placebo in addition to standard of care. This will be assessed using the 11-point numerical pain rating scales (NRS-11) from post-operative day 1 to 7.

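### Sections 1.2.1 and 12.1 set the primary pain comparison over post-operative days 1 to 7, but Section 12.2 states and sizes it for day 7 alone, and the two are not reconciled

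*Combined protocol and SAP*

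**What the plan says.** **POD 1 to 7.** Section 1.2.1, under the primary objectives, says of the pain comparison: "This will be assessed using the 11-point numerical pain rating scales (NRS-11) from post-operative day 1 to 7". Section 12.1 opens its endpoint paragraph with "Our primary endpoint will be to compare participant reported pain between participants receiving gabapentin and those receiving placebo in addition to standard of care" and follows it with the same POD 1 to 7 sentence.

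**Day 7.** Section 12.2 restates the primary objective as pain "between subjects who received Gabapentin and controls who received placebo on day-7 post-scrotal surgery". Its sample-size paragraph says "a goal is to detect a two-point difference (reduction) in the day-7 pain score between the two groups", using a two-sample t-test at two-sided 0.05 with an SD of 2.9, and allows for "loss to follow up and drop-out at a rate of 25" per cent.

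**Listed pain analyses (12.2).**
- A t-test or Wilcoxon test, as appropriate, on "participant-reported pain scores on day 7 post-scrotal surgery between the two arms".
- A repeat at day 1: "Similar analyses will also be completed on the NRS-11 pain score, narcotic use, and reported adverse events on day-1 post-scrotal surgery".
- A GEE: "modeling will also be performed to compare NRS pain scores, assessed over all post-operative days 1 to 7".

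All p-values are judged at two-sided 0.05. No analysis is labelled primary, and there is no testing order or multiplicity rule.

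**Elsewhere.** The protocol summary (Section 1) gives the primary objective only as pain scores, with no time point. Section 3.4 ends participation at the POD 7 assessment, which fits either reading.

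**The concern.** A day-7 score and a POD 1 to 7 course are different quantities, and current sections attach the word primary to each. Sections 12.1 and 12.2 belong to the same statistical chapter, so this is not a summary shortening a fuller text.

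The choice can change the answer. Scheduled dosing ends on POD 3 (Sections 6.1 and 12.1), so POD 1 to 7 includes the dosing days, while day 7 comes about four days after them. Missing data also act differently: Section 12.2 says the GEE accommodates participants with some scores missing, whereas the day-7 test needs a day-7 score.

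An author who reported the GEE as primary could cite Sections 1.2.1 and 12.1, and one who reported the day-7 test could cite Section 12.2. Both would be following the protocol. If that choice were made after the results were seen, the 5% error rate would no longer hold.

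**Working it through.** **1. Which endpoint the sample size supports.** Inputs from Section 12.2: difference 2, SD 2.9, two-sided alpha 0.05, power 80%, loss 25%.

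- Normal approximation: n = 2 × (1.96 + 0.84)² × (2.9/2)² = 2 × 7.849 × 2.1025 ≈ 33.005, so 34 per arm. The exact t-test calculation gives 33.99, also 34.
- Adding 25%: 34 × 1.25 = 42.5, so 43 per arm and 86 in total. This matches the plan.

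The stated figure therefore rests on the day-7 two-sample t-test. No calculation in the documents supports a POD 1 to 7 comparison.

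**2. Evaluable numbers.** With 25% lost, 43 × 0.75 = 32.25, so 32 per arm. Day-7 power for 2 points is 77.5% with 32 per arm and 88.5% with 43.

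**3. A model for comparing the two analyses.** The documents give no between-day correlation and no effect by day. Assumed: normal scores with SD 2.9 on each of 7 days, a common correlation ρ between days, and the GEE approximated by a t-test on the 7-day mean. Then SD of the mean = 2.9 × √((1 + 6ρ)/7).

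| | ρ = 0.3 | 0.5 | 0.7 | 0.9 |
|---|---|---|---|---|
| SD of 7-day mean | 1.83 | 2.19 | 2.50 | 2.77 |
| False-positive rate if day 7 or the 7-day mean may decide, 32 per arm | 8.7% | 8.0% | 7.5% | 6.4% |
| The same, 43 per arm | 8.6% | 8.2% | 7.3% | 6.4% |
| Exactly one of the two significant, constant 2 points, 32 per arm | 21.8% | 18.7% | 14.0% | 7.4% |
| – 7-day mean only | 21.7% | 18.0% | 12.4% | 5.4% |
| – day 7 only | 0.1% | 0.7% | 1.6% | 2.0% |
| Exactly one of the two significant, constant 2 points, 43 per arm | 11.3% | 10.5% | 8.4% | 4.7% |
| Power of 7-day mean, constant 2 points, 32 per arm | 99.0% | 94.9% | 88.3% | 81.1% |

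The false-positive and disagreement rows are simulated (200,000 trials per setting for the 32-per-arm false-positive row, where each single test rejected in 4.9% to 5.1%). The power row is exact for the t-test.

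**4. A short-lived effect.** If 2 points applied on POD 1 to 3 only, the weekly average would be (3 × 2)/7 = 0.86. With 32 per arm, 80% power needs an average of 1.30 to 1.97 points over the correlations above, so the weekly analysis would be underpowered. The day-7 difference would be zero, so the day-7 test would miss the effect altogether.

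**The case against.** The best defence is that Section 12.2 already settles the matter. It is the most specific text, states the primary objective at day 7, names a two-sample t-test in the sample size, lists the day-7 test first, and introduces the day-1 tests and the GEE as additions. On this view the POD 1 to 7 sentence describes only the diary's measurement window.

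Much of this stands. A reader might infer that the plan gives no indication of its deciding test, and the documents do not support that: Section 12.2 points fairly clearly to day 7. But the lean is an inference. Section 12.1 attaches the POD 1 to 7 sentence directly to the words primary endpoint, and the GEE is the only listed analysis that covers that period. Even within the day-7 reading, the test is left as t-test or Wilcoxon.

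Three other strong readings also go too far.
- Day 1 could be counted as a third route to success, which would raise the error rate further. No section offers day 1 as primary.
- A steep fade in effect would make the two analyses disagree far more often. The documents give no such profile.
- It could be said that 5% is protected only by naming a single test. A prespecified hierarchy or alpha split would protect it as well.

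**Conclusion.** The inconsistency is in the current text, no other section resolves it, and it must be fixed before unblinding. It consists of two time frames for one primary comparison, with a lean to day 7 and no stated rank for the analysis that covers POD 1 to 7.

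If success could be claimed on either analysis, the false-positive rate is about 6.4% to 8.7% instead of 5%. Under a constant 2-point effect with 32 evaluable per arm, the two verdicts differ in about 7% to 22% of trials. Both ranges depend on the assumed equal SD, normality, common correlation of 0.9 down to 0.3, and the 7-day mean standing in for the GEE. The contradiction itself depends on none of these.

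A reader might also infer that one endpoint is simply the better powered. The documents do not support this, because the ranking depends on a correlation and an effect-over-time that they do not state.

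**What to change.** Before unblinding, make Sections 1.2.1, 12.1 and 12.2 state the same primary endpoint. Name one primary analysis, or a prespecified hierarchy or alpha split that holds 5% overall, and label the remaining pain tests secondary.

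- **If day 7 is kept.** This matches the existing sample size. Amend 1.2.1 and 12.1, choose the t-test or Wilcoxon in advance, and define the day-7 score from that day's two 12-hourly surveys (Section 11.1). The downside is that an effect limited to the dosing days would be missed.
- **If POD 1 to 7 is chosen.** Name the GEE treatment contrast as the primary analysis and restate power with an explicit correlation and effect-over-time assumption. Under a constant 2-point effect with 32 per arm, the weekly mean has about 81% to 99% power against 77.5% for day 7. Its power is lower if the effect is short-lived. The downside is that this replaces the only endpoint the plan has sized.

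Either way the cost is an IRB-approved amendment, plus a new power statement under the second option. No new data or visits are needed, because the diary already collects scores over POD 1 to 7.

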## 1. Protocol Summary

Full Title:	Multi-modal Analgesia to Reduce Narcotics After Scrotal Surgery
Short Title:	Narcotic Reduction After Surgery
Clinical Phase:	III
Principal Investigator:	[name]
Study Description:	The use of non-narcotic multi-modal analgesia to be used in the pre-operative, peri-operative and post-operative period to reduce or potentially eliminate narcotic usage following scrotal surgery. We have shown that the use of anti-inflammatories in the peri-operative period reduce both pain and narcotic use. Our hypothesis is that adding another agent in the multi modal pathway will further reduce pain and potentially reduce narcotic usage.
Sample Size:	N= 86 (43 participants in each arm)
Enrollment:	This study will enroll 86 participants but will screen 114 participants accounting for an approximate 25% screening failure rate.
Study Population:	Participants undergoing microsurgical testicular sperm extraction for non-obstructive azoospermia.
Enrollment Period:	2 years.
Study Design:	Double-blind, placebo-controlled, randomized trial Two study arms (43 participants per arm) Addition of gabapentin pre- and post-operatively
Description of Sites/	
Facilities Enrolling	
Participants:	This will be a single center study at Weill Cornell Medicine/New York Presbyterian Hospital.
Study Duration:	December 31, 2023
Participant Duration:	7 days.
Study Agent/Device Name	
Intervention Description:	Arm #1 – Gabapentin 600mg taken pre-operatively and 300mg taken three times a day for 3 days. Arm #2 – Placebo taken pre-operatively and three times a day for 3 days.
Primary Objective:	Pain scores
Secondary Objectives:	Narcotic consumption
Exploratory Objectives:	Symptom modification (ie. nausea)
Endpoints:	Numerical pain rating scale Narcotic prescription usage

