### **7.11 Measures to Minimize Bias: Randomization and Blinding**

Permuted blocked randomization will be performed. A series of randomized blocks with a defined block size will be generated with a 1:1 allocation ratio to allow for an equal number of participants in the study drug and placebo groups. A statistician from the Weill Cornell CTSC Biostatistics, Epidemiology and Research Design (BERD) Core will create the randomization list and will not be involved with the study statistician(s). The randomization list will also reside in the Research Pharmacy. Only the BERD statistician and the Research Pharmacy will have a copy of the blocked randomization list and will know the true meaning of the block assignments. If unbinding is necessary, the BERD statistician (or Research Pharmacy) can immediately determine whether or not the participant received the study drug or placebo.

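### 43 per arm is given both as the number for 80% power and as the number after 25% loss; with that loss the trial falls short of 80%

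*Combined protocol and SAP*

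**What the plan says.** Section 12.2 plans to "detect a two-point difference (reduction) in the day-7 pain score between the two groups" and says that "a sample size of 86 participants (43 per arm) will yield a power of 80% when using a two-sample t-test". On variability it adds: "This calculation assumes a standard deviation of 2.9". The significance level is stated twice, the second time as "All p-values will be two-sided with statistical significance evaluated at the 0.05 alpha level". Section 7.11 sets equal allocation.

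The sentence after the power claim reads: "To account for potential loss to follow up and drop-out at a rate of 25%, each arm will require 43 study participants". The total given there is again 86. No number before inflation appears anywhere.

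Sections 1 and 12.1 give 86 as the number enrolled and randomised, so nothing is added later. Section 1 has a second 25%, for screening: "This study will enroll 86 participants but will screen 114 participants accounting for an approximate 25% screening failure rate". Section 12.2 closes its sample-size text on accrual: "we plan to accrue and complete the study in 29 months (i.e. ~9 study participants per month".

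**The concern.** One number is asked to do two jobs. If 43 per arm is the number that must be analysed to reach 80% power, nothing has been added for loss. If 43 already includes the allowance for loss, fewer than 43 will be analysed, and 43 is not itself the number that gives 80%. A reader cannot tell whether the planned power is about 88%, 80% or 78%.

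The paragraph is the sole basis for the sample size, so ethics, monitoring and publication reviewers will judge from it whether the trial can answer its question. The accrual sentence has a similar fault, because its monthly rate and its duration do not multiply to the planned total.

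**Working it through.** **Inputs (Section 12.2 unless noted).** Difference 2 points on day 7; SD 2.9; two-sided alpha 0.05; power 80%; two-sample t-test; 1:1 allocation (Section 7.11); loss 25%; 43 per arm randomised.

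**Step 1: evaluable number for 80% power.** By the normal approximation, n = 2 x [SD x (1.960 + 0.842) / difference]² = 2 x [2.9 x 2.802 / 2]² = 33.0045, which rounds up to 34. The t-test calculation (noncentral t, 2n - 2 degrees of freedom, noncentrality (2/2.9) x √(n/2)) gives n = 33.99, also 34 per arm.

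**Step 2: reproducing the plan's 43.**
- 34 x (1 + 0.25) = 42.5, rounded up to 43. This matches.
- 34 / (1 - 0.25) = 45.3, rounded up to 46. This does not match.
- No inflation gives 34, a one-sided test gives 27, and 90% power without inflation gives 46. None matches.

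The plan's figure is therefore recovered only by multiplying by 1.25. To keep 34 after losing a quarter, one must divide by 0.75.

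**Step 3: power under each reading (t-test).**

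| Evaluable per arm | How it arises | Power |
|---|---|---|
| 43 | no loss | 88.5% |
| 34 | 43 less 9 (9/43 = 20.9% loss) | 80.0% |
| 33 | 43 less 25%, rounded up | 78.8% |
| 32.25 | 43 x 0.75 | 77.8% |
| 32 | 43 less 25%, rounded down | 77.5% |

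Treating loss as random at 25% in each arm and averaging over the possible numbers remaining also gives 77.5%. By the normal approximation, power is 78.8% at 32 and 79.1% at 32.25. The difference detectable with 80% power at 32 per arm is 2.06 points.

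**Step 4: the correctly inflated size.** 46 per arm (92 in total) leaves 46 x 0.75 = 34.5, with power 80.0% at 34 and 81.2% at 35. The gap from the plan is 3 per arm, 6 in total.

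**Step 5: whether another section makes up the loss.**
- Screening: 86 / 0.75 = 114.7, against 114 stated. This loss falls before randomisation (Section 4.5 defines it so) and cannot also cover drop-out. The division form was apparently used here.
- Replacement: Section 8.2 permits, but does not require, replacing those randomised and not treated. Treated participants who withdraw are not replaced.
- Longitudinal model: the GEE in Section 12.2 can use participants with some missing scores, but the power claim is for the day-7 t-test, which needs a day-7 score.

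**Step 6: accrual.** 9 x 29 = 261, about three times 86. Conversely, 86 / 29 = 3.0 per month, and 86 / 9 = 9.6 months.

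**The case against.** The strongest reply is that the two sentences form one statement: 86 are recruited, a quarter may be lost, and power is about 80%. The text does not call the 43 evaluable, and Sections 1 and 12.1 do present 86 as the number randomised. On that reading the 88.5% is beside the point and the only fault is the inflation formula. The effect is then slight. The detectable difference moves from 2.00 to 2.06 points, and with 32 per arm 80% power returns if the SD is 2.81 (2.9 x 2.00 / 2.06), while 2.9 is itself a planning value from an earlier study. Replacing untreated participants could also bring net loss nearer the 20.9% at which 80% holds.

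Much of this stands. The shortfall is modest, and the factor of 1.25 is inferred from an exact match, since the documents print neither the 34 nor the method. The screening rate in Section 1 is labelled correctly and is no error. The accrual mismatch has no bearing on power. The charitable reading still does not rescue the claim: at the stated loss rate the stated test has less than 80% power, and replacement is optional and excludes treated withdrawals.

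**Conclusion.** The concern holds. On the plan's own inputs, 43 per arm gives 88.5% power with no loss and 77.5% to 77.8% with the stated 25% loss. It gives 80% only if loss is no more than 20.9%. The number that allows for 25% loss is 46 per arm, 92 in total, against the 86 stated. The power shortfall is about 2 to 2.5 percentage points, so the trial is not badly underpowered; the fault is that the stated power and the stated allowance for loss cannot both be true of 86. Separately, the accrual rate and duration disagree threefold.

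These results assume the t-test on day-7 scores, equal loss in the two arms, and the planned difference and SD. They do not cover the Wilcoxon test that Section 12.2 allows as an alternative.

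**What to change.** Replace the two sample-size sentences in Section 12.2 with text along these lines:

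> Thirty-four evaluable participants per arm give 80% power (two-sample t-test, two-sided 0.05, difference 2 points, SD 2.9). With 43 randomised per arm, power is 88.5% with no loss, 80% with 21% loss, and about 78% with 25% loss.

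This is a wording change that adds no participants; its only cost is a slightly less favourable stated power. If the sponsor wants 80% at 25% loss, the alternative is 46 per arm (92 in total). That means 6 more participants, matching changes in Sections 1 and 12.1, and about 123 screened at the same screening rate (92 / 0.75 = 122.7).

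Under either option, keep the post-randomisation loss distinct from the screening rate in Section 1. For 86 participants, restate accrual as about 3 per month over 29 months, or about 10 months at 9 per month, whichever is meant.
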